## 2.5.3 Handling of missing values/censoring/discontinuations

All attempts will be made to ensure that the database contains full information for all safety data. No imputation will be applied for missing data except for missing dates (See Section 5.1).

## 2.5.4 Supportive analyses

Not applicable.

## 2.6 Analysis of the key secondary objective

Not applicable

## 2.6.1 Key secondary endpoint

Not applicable.

## 2.6.2 Statistical hypothesis, model, and method of analysis

Not applicable.

## 2.6.3 Handling of missing values/censoring/discontinuations

Not applicable.

Novartis	Confidential	Page 29
SAP	22-Feb-2022 (1:27)	CLEE011A2404

## 2.7 Analysis of secondary efficacy objective(s)

The secondary efficacy objective of this study is to assess the clinical efficacy of ribociclib + letrozole in Full Analysis Set.

The following endpoints as defined by RECIST1.1 will be used to evaluate the secondary objectives:

- Time-to-Progression (TTP) based on investigators' assessment
- Overall response rate (ORR) for patients with measurable disease at baseline
- Clinical Benefit Rate (CBR) (including patients with CR, PR, SD/Non-CR/Non-PD > 24 weeks)

## 2.7.1 Secondary endpoints

## Time to progression (TTP)

Time to progression is defined as time from date of start of treatment to the date of event defined as the first documented progression or death due to underlying cancer (Novartis RECIST Guideline v 3.2). Patients with symptoms of rapidly progressing disease without radiologic evidence will be classified as progression only when clear evidence of clinical deterioration is documented and/or patient discontinued due to 'Disease progression' or death due to study indication. When there is no documentation of radiologic evidence of progression, and the patient discontinued for 'Disease progression' due to documented clinical deterioration of disease, the date of discontinuation is used as date of progression.

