- Adjustments to study treatment due to toxicity that result in discontinuation. Please refer to Section 6.3
- Use of prohibited medication. Please refer to Section 6.4.3
- Any other protocol deviation that results in a significant risk to the patient's safety.

Patients who discontinue study treatment should undergo an End of Treatment (EOT) visit followed by a 30-day safety follow-up.

At EOT visit, all the assessments as listed in Table 7-1 will be performed. If the decision to discontinue the patient occurs at a regularly scheduled visit, that visit may serve as the EOT visit rather than having the patient return for an additional visit.

The investigator or his/her delegate must also contact the IRT to register the patient's discontinuation from study treatment within 2 days of EOT visit.

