- Date of discontinuation is the date of the end of treatment visit.
- Date of last contact is defined as the last date the patient was known to be alive. This corresponds to the latest date for either the visit date, lab sample date or tumor assessment date. If available, the last known date patient alive from the survival follow-up page is used. If no survival follow-up is available, the date of discontinuation is used as last contact date.
- Date of secondary anti-cancer therapy is defined as the start date of any additional (secondary) antineoplastic therapy or surgery.

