14.3.28 Sensitivity analyses

This section outlines the possible event and censoring dates for progression, as well as addresses the issues of missing tumor assessments during the study. For instance, if one or more assessment visits are missed prior to the progression event, to what date should the progression event be assigned? And should progression event be ignored if it occurred after a long period of a patient being lost to follow-up? It is important that the protocol and RAP specify the primary analysis in detail with respect to the definition of event and censoring dates and also include a description of one or more sensitivity analyses to be performed.

Based on definitions outlined in Section 14.3.25, and using the draft FDA guideline on endpoints (Clinical Trial Endpoints for the Approval of Cancer Drugs and Biologics, April 2005) as a reference, the following analyses can be considered:

Situation		Options for end-date (progression or censoring) ¹ (1) = default unless specified differently in the protocol or RAP	Outcome	
А	No baseline assessment	(1) Date of randomization/start of treatment ³	Censored	
В	Progression at or before next scheduled assessment	 (1) Date of progression (2) Date of next scheduled assessment² 	Progressed Progressed	
C1	Progression or death after exactly one missing assessment	 (1) Date of progression (or death) (2) Date of next scheduled assessment² 	Progressed Progressed	
C2	Progression or death after two or more missing assessments	 (1) Date of last adequate assessment² (2) Date of next scheduled assessment² (3) Date of progression (or death) 	Censored Progressed Progressed	
D	No progression	(1) Date of last adequate assessment	Censored	

Table 14 7	Options for event dates	used in DES TTD	duration of reasons
	Options for event dates	useu III FF3, I IF	, uuralion or response

Situation		Options for end-date (progression or censoring) ¹ (1) = default unless specified differently in the protocol or RAP	Outcome
E	Treatment discontinuation due to 'Disease progression' without documented progression, i.e. clinical progression	(1) Ignore clinical progression and follow situations above	As per above situations
	based on investigator claim	(2) Date of discontinuation (visit date at which clinical progression was determined)	Progressed
F	New anticancer therapy given	(1) Ignore the new anticancer therapy and follow situations above (ITT approach)	As per above situations

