14.3.31 End of treatment phase completion

Patients **may** voluntarily withdraw from the study treatment or may be taken off the study treatment at the discretion of the investigator at any time. For patients who are lost to follow-up, the investigator or designee should show "due diligence" by documenting in the source documents steps taken to contact the patient, e.g., dates of telephone calls, registered letters, etc.

The end of treatment visit and its associated assessments should occur within 7 days of the last study treatment.

Patients may discontinue study treatment for any of the following reasons:

- Adverse event(s)
- Lost to follow-up
- Physician decision
- Pregnancy
- Protocol deviation
- Technical problems
- Subject/guardian decision
- Progressive disease
- Study terminated by the sponsor
- Non-compliant with study treatment
- No longer requires treatment
- Treatment duration completed as per protocol (optional, to be used if only a fixed number of cycles is given)

Death is a reason which "must" lead to discontinuation of patient from trial.

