#### 2.7.3 Handling of missing values/censoring/discontinuations

TTP will be censored at the date of the last adequate tumor assessment if no TTP event is observed prior to the analysis cut-off date or the date when a new anti-neoplastic therapy or another investigational treatment for cancer is started, whichever occurs earlier. The censoring date will be the date of last adequate tumor assessment.

The date of last adequate tumor assessment is the date of the last tumor assessment with overall lesion response of CR, PR or SD before an event or a censoring reason occurred. In this case the last tumor evaluation date at that assessment will be used. If no post-baseline assessments are available (before an event or a censoring reason occurred) then the start date of treatment will be used.

In particular, TTP will be censored at the last adequate tumor assessment if one of the following occurs: absence of event, the event occurred after two or more missing tumor assessments. The term "missing adequate tumor assessment" is defined as a tumor assessment (TA) not performed or tumor assessment with overall lesion response of "UNK". The rule to determine number of missing TAs is based on the time interval between the date of last adequate tumor assessment and the date of an event.

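### The date of clinical (non-radiologic) progression has two meanings in the documents; under one of them, a progression recognised before a therapy switch is lost from TTP as back-dated censoring

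*SAP*

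**What the plan says.** SAP 2.7.1 and protocol 10.5.1 both count documented clinical deterioration without radiologic evidence as progression. When the patient stops treatment for that reason, "the date of discontinuation is used as date of progression". Neither section says which calendar date is meant.

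The protocol's RECIST appendix gives two answers:

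- Section 14.3.26, as a general definition: "Date of discontinuation is the date of the end of treatment visit".
- Table 14-7 in 14.3.28, for treatment stopped because of clinical progression (situation E, option 2): "Date of discontinuation (visit date at which clinical progression was determined".

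On EOT timing, 14.3.31 says: "The end of treatment visit and its associated assessments should occur within 7 days of the last study treatment". Protocol 7.1.5 adds that, if discontinuation is decided at a scheduled visit, "that visit may serve as the EOT visit rather than having the patient return for an additional visit".

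SAP 2.7.3 censors TTP when no event is observed before the cut-off date or "the date when a new anti-neoplastic therapy or another investigational treatment for cancer is started, whichever occurs earlier". It continues: "The censoring date will be the date of last adequate tumor assessment". With no post-baseline assessment, "then the start date of treatment will be used". There is no exception for clinical progression recognised before the switch.

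For new therapy, Table 14-7 (situation F, option 1) has the opposite default, which is to ignore it, and 14.3.28 requires the handling to be specified in the protocol. Protocol section 10 gives no such rule for TTP. SAP section 4 declares no change from the protocol.

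**The concern.** The clinical-progression rule exists so that patients who deteriorate too fast for a scan still count as having progressed. A patient in that position may also start the next treatment within days. If the event date is the EOT visit and new therapy starts on or before it, the event falls on the wrong side of the SAP 2.7.3 cut and is discarded. The patient then contributes censored time ending at an earlier scan, or on Day 1.

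That censoring is informative, because it happens as a result of the patient having progressed. The study has a single arm, so no comparator shares the bias. Two programmers could also follow the documents faithfully and derive an event and a censored record for the same patient.

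**Working it through.** The plan states no figure on this point, so there is none to reproduce. The check has two parts: the rules applied literally to example patients, and an illustration of the effect on the Kaplan-Meier median.

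**Rules on example patients.** An event counts if its date is strictly before the start of new therapy; otherwise the record is censored at the last adequate scan, or at Day 1 if there is none. The cut-off date is taken as later than all dates shown. The days are invented. Scans are 12-weekly (Days 85 and 169), as the protocol recommends, and no scan shows progression before the switch. No example has two missed assessments, so that separate censoring rule is not triggered.

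| Patient | Last dose | New therapy | EOT visit | Event dated at EOT visit |
|---|---|---|---|---|
| A: stable scans Days 85, 169 | Day 235 | Day 238 | Day 242 | Censored, Day 169 |
| B: as A, later switch | Day 235 | Day 243 | Day 242 | Event, Day 242 |
| C: as A, switch on EOT day | Day 235 | Day 242 | Day 242 | Censored, Day 169 |
| D: no post-baseline scan | Day 50 | Day 53 | Day 57 | Censored, Day 1 |

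For A the event disappears and follow-up is cut by 242 − 169 = 73 days. C is censored because the SAP requires the event to come before the switch. D, the fastest progressor, loses all follow-up.

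Under the alternatives, patient A becomes:

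- Dated at the determination visit (taken as Day 235): event at Day 235.
- New therapy ignored (situation F, option 1): event at Day 242.
- Determination date unrecorded, using the earlier of EOT visit and new-therapy start: min(242, 238), so event at Day 238.

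**Effect on the median.** The share of TTP events lost, L, is not in the documents; 1% to 10% is assumed. The 25.3-month median is the PFS of the earlier phase III ribociclib + letrozole arm (protocol 1.1.1), used as a stand-in for TTP. For an exponential curve, losing a random share L multiplies the event rate by (1 − L), so the median is about 25.3 / (1 − L). A simulation (exponential TTP, 18 to 34 months of follow-up, 12-weekly scans, lost events censored at the preceding scan) gave the other columns.

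| L | 25.3 / (1 − L) | Simulated median | Simulated 12-month event-free rate |
|---|---|---|---|
| 0 | 25.3 | 25.3 | 71.9% |
| 1% | 25.6 | 25.5 | 72.2% |
| 2% | 25.8 | 25.8 | 72.4% |
| 5% | 26.6 | 26.5 | 73.1% |
| 10% | 28.1 | 28.0 | 74.3% |

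The simulated medians sit slightly below the formula at the larger shares, mainly because back-dated patients also leave the risk set a little early. With an assumed median of 18 months, the simulated medians for 1, 2, 5 and 10% lost are 18.1, 18.3, 18.9 and 19.8 months. In every run the shift is towards longer TTP.

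**The case against.** The strongest reply is that the loss depends on reading two phrases the unfavourable way. The EOT-visit meaning comes from a general appendix definition. Table 14-7 addresses this very situation and points to the determination visit; on that reading the event normally precedes any switch and survives. SAP 2.7.3 also speaks of an event being observed, and deterioration documented before the switch could be called observed whatever date is assigned to it.

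The exposed window is narrow. It is at most 7 days after the last dose, and nil when the decision visit serves as the EOT visit. Protocol 7.2.1 requires prompt imaging on clinical suspicion of progression, Table 7-3 asks for imaging at EOT, and protocol 4.1 strongly recommends a scan before a switch. All of these reduce the number of clinical-only events. TTP is a descriptive secondary endpoint, so no alpha, power or decision rule is touched.

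Most of this stands, and it limits the size of the point. It does not remove it: the SAP does not choose between the two definitions, a pre-switch scan is not mandatory, and Table 7-1 collects at the EOT visit any antineoplastic therapy given since discontinuation, so a start before that visit is foreseen. A first radiologic progression on an EOT scan after the switch would also be censored, and only an analysis that ignores new therapy recovers it.

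**Conclusion.** The point holds as an ambiguity with a one-way consequence. The appendix gives two dates for the same event. Under the EOT-visit date, combined with SAP 2.7.3, a recognised clinical progression becomes censoring at the last adequate scan or at treatment start whenever new therapy begins on or before the EOT visit. Under the determination-visit date the event usually survives.

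The bias is towards longer TTP. The number affected cannot be derived from the documents and is probably small. The 25.5 months at 1% lost is an illustration resting on an assumed share, an exponential curve and a borrowed PFS median; the higher rows show sensitivity and are not expected values.

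A reader might infer more than this:

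- That the plan definitely dates clinical progression at the EOT visit. Table 14-7 contradicts that.
- That the median is inflated by a month or more. That needs a share of lost events for which the documents give no basis.
- That ECOG PS 2 or visceral-disease subgroups are hit hardest. Nothing in the documents supports this.

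Separately, censoring at new therapy departs from the appendix default, and SAP section 4 does not acknowledge it.

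**What to change.** 1. In SAP 2.7.1, date clinical progression at the visit where it was determined, as Table 14-7 (situation E, option 2) already words it. State that it counts as an event when determined on or before the start of new therapy.
2. If the determination date is not recorded and disease progression is the recorded reason for stopping, keep the event and date it at the earlier of the EOT visit and the start of new therapy. Do not fall back on the last study-drug dose. SAP 2.1.3 separates ribociclib from study treatment as a whole, and a last ribociclib dose can precede recognition by the rest week or an interruption, which would date progression too early.
3. Reconcile Appendix 14.3.26, Table 14-7 and SAP 2.7.1 so that one definition governs this rule.
4. Add a TTP sensitivity analysis that ignores new therapy (Table 14-7, situation F, option 1), and record the departure from that default in SAP section 4. If the Core Phase TTP has already been reported, the revised dating can be run as a documented additional analysis.

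The cost is SAP wording, a small derivation and one extra table. The documents do not show whether the determination date is a separate data field, so the fallback in item 2 may be needed often. TTP may be reported slightly shorter.

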## Overall response rate (ORR)

Overall response rate is defined as the proportion of patients with best overall response (BOR) of complete response (CR) or partial response (PR) according to RECIST 1.1 (see Appendix 3 of the study protocol). ORR will be calculated based on the FAS in patients with measurable disease at baseline using local investigators review of tumor assessment data. Tumor assessments performed before the start of any further antineoplastic therapy (i.e. any additional secondary antineoplastic therapy or surgery) will be considered in the assessment of BOR.

Palliative radiotherapy is allowed as per protocol. If palliative radiotherapy is initiated after the start of study treatment, the reason for its use must be clearly documented and progression as per RECIST 1.1 must be ruled out. For example, palliative radiotherapy given in the trial for analgesic purposes or for lytic lesions at risk of fracture will not be considered as cancer therapy for the assessment of BOR analyses.

## Clinical benefit rate (CBR)

CBR is defined as the proportion of patients with a best overall response (BOR) of confirmed CR or PR, or SD lasting 24 weeks or longer, according to RECIST 1.1 criteria. A patient will be considered to have SD for 24 weeks or longer if a SD response is recorded at 23 weeks or later from enrollment, allowing for the  $\pm 1$  week visit window for tumor assessments. Patients with only non-measurable disease at baseline will be part of the analysis and will be included in the numerator only if they achieve a complete response or have a 'Non-CR/Non-PD'

Novartis	Confidential	Page 30
SAP	22-Feb-2022 (1:27)	CLEE011A2404

response 23 weeks or more after enrollment. CBR will be calculated using the FAS based on the investigators' tumor assessments.

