10.5 Secondary objectives

10.5.1 Secondary objective(s)

The secondary objective of this study is to assess the clinical efficacy of ribociclib + letrozole (+ goserelin or leuprolide) in Full Analysis Set.

The following endpoints as defined by RECIST1.1 will be use key secondary objectives:

- Time-to-Progression (TTP) based on investigators' assessment
- Overall response rate (ORR) for patients with measurable disease
- Clinical Benefit Rate (CBR) (including patients with CR, PR, SD/NCRNPD>24 weeks)

Time to progression (TTP) is defined as time from date of start of treatment to the date of event defined as the first documented progression or death due to underlying cancer (Appendix 14.3: Novartis RECIST Guideline v 3.2). Patients with symptoms of rapidly progressing disease without radiologic evidence will be classified as progression only when clear evidence of clinical deterioration is documented and/or patient discontinued due to 'Disease progression' or death due to study indication. When there is no documentation of radiologic evidence of progression, and the patient discontinued for 'Disease progression' due to documented clinical deterioration of disease, the date of discontinuation is used as date of progression.

Overall response rate (ORR) is defined as the proportion of patients with best overall response of complete response (CR) or partial response (PR) according to RECIST 1.1.

Clinical benefit rate (CBR) is defined as the proportion of patients with a best overall response of complete response (CR), or partial response (PR) or an overall lesion response of stable disease (SD), lasting as per local review, for a duration of at least 24 weeks. CR, PR and SD are defined according to RECIST 1.1 (see Appendix 14.3 for details)

The distribution of TTP will be estimated using the Kaplan-Meier method. The median TTP along with 95% confidence intervals will be presented. Proportions of patients with ORR and CBR as assessed by investigator will be calculated and presented along with the approximate 95% confidence intervals using Clopper and Pearson (1934) exact method.

In addition, PRO will be assessed using FACT-B instrument (See Section 10.5.4).

During Extension Phase, frequency of AEs & SAEs will be summarized.

The proportion of patients with clinical benefit as assessed by investigator will be reported at each scheduled visit during Extension Phase.

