- PR = at least two determinations of PR or better at least 4 weeks apart before progression (and not qualifying for a CR) where confirmation required or one determination of PR prior to progression where confirmation not required
- SD = at least one SD assessment (or better) > 6 weeks after randomization/start of treatment (and not qualifying for CR or PR).
- PD = progression ≤ 12 weeks after randomization/ start of treatment (and not qualifying for CR, PR or SD).
- UNK = all other cases (i.e. not qualifying for confirmed CR or PR and without SD after more than 6 weeks or early progression within the first 12 weeks)

The time durations specified in the SD/PD/UNK definitions above are defaults based on a 6 week tumor assessment frequency. However these may be modified for specific indications which are more or less aggressive. In addition, it is envisaged that the time duration may also take into account assessment windows. E.g. if the assessment occurs every 6 weeks with a time window of \pm 7 days, a BOR of SD would require a SD or better response longer than 5 weeks after randomization/start of treatment.

Overall lesion responses of CR must stay the same until progression sets in, with the exception of a UNK status. A patient who had a CR cannot subsequently have a lower status other than a PD, e.g. PR or SD, as this would imply a progression based on one or more lesions reappearing, in which case the status would become a PD.

Once an overall lesion response of PR is observed (which may have to be a confirmed PR depending on the study) this assignment must stay the same or improve over time until progression sets in, with the exception of an UNK status. However, in studies where confirmation of response is required, if a patient has a single PR (\geq 30% reduction of tumor burden compared to baseline) at one assessment, followed by a <30% reduction from baseline at the next assessment (but not \geq 20% increase from previous smallest sum), the objective status at that assessment should be SD. Once a confirmed PR was seen, the overall lesion response should be considered PR (or UNK) until progression is documented or the lesions totally disappear in which case a CR assignment is applicable. In studies where confirmation of response is not required after a single PR the overall lesion response should still be considered

PR (or UNK) until progression is documented or the lesion totally disappears in which case a CR assignment is applicable.

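### SAP 2.7.1 times stable disease for CBR from an undefined enrollment date instead of start of treatment, and asks for confirmed response in CBR while ORR states no confirmation

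*SAP*

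**What the plan says.** SAP 2.7.1 defines CBR through a "best overall response (BOR) of confirmed CR or PR, or SD lasting 24 weeks or longer". It treats SD as having lasted 24 weeks "if a SD response is recorded at 23 weeks or later from enrollment", and explains the week below 24 by a one-week visit window for tumor assessments. Patients with only non-measurable disease count if they reach CR or have a Non-CR/Non-PD "response 23 weeks or more after enrollment".

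The two neighbouring endpoints in SAP 2.7.1 are written differently. ORR is the proportion with a "best overall response (BOR) of complete response (CR) or partial response (PR) according to RECIST 1.1", with no mention of confirmation. For TTP: "Time to progression is defined as time from date of start of treatment to the date of event".

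Protocol 10.5.1 asks for SD lasting at least 24 weeks, names no time origin, says nothing about confirmation, and refers to Appendix 14.3 for the response definitions. SAP Section 4 declares no change from the protocol's analyses.

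**The concern.** A programmer needs a date from which to count the 23 weeks, and the SAP names one it does not define. If that date is consent, part of the screening period is credited as disease control, and two programmers could classify the same patient differently. Other tumor endpoints in the same section run from first treatment, so CBR would rest on a different clock from TTP. On confirmation, a patient could be a responder in one table and lack clinical benefit in the next. At stake are the consistency and reproducibility of one secondary efficacy proportion, together with its exact confidence interval.

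**Working it through.** **1. The SAP's own figure.** 24 weeks − 1 week = 23 weeks = 23 × 7 = 161 days. The cut-off reproduces.

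**2. What enrollment means.** The protocol's Glossary of terms places it at informed consent. Protocol 6.5.1 speaks of enrollment for screening, with the subject number assigned on signing consent. Against that, protocol 7.1.2.2 calls a consented screen failure not enrolled, and SAP 2.1.1 speaks of enrolled patients completing 18 months of treatment. The study-day rule in SAP 2.1.3 does not settle it, because its reference date is the start of study, which is also undefined.

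**3. What the related rules use.**
- Protocol 14.3.17: SD as best response needs "at least one SD assessment (or better) > 6 weeks after randomization/start of treatment". Its window-adjusted example has the same origin.
- Protocol 14.3.24: duration of stable disease takes its start date from TTP. This is the most direct parallel.
- Protocol 14.3.26: time-to-event variables other than duration of response start at randomization or treatment start.
- Protocol 7.2.1: scans are scheduled from the first dose.

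The study is single-arm and not randomized, so all of these mean treatment start.

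**4. Effect if enrollment means consent.** The documents do not give the lead L from consent to first dose. The 28-day screening window in protocol 7.1.2 suggests an assumed range of 1 to 28 days. Cut-off in days after first dose = 161 − L.

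| L (days) | Cut-off day | Weeks on treatment |
|---|---|---|
| 1 | 160 | 22.9 |
| 7 | 154 | 22 |
| 14 | 147 | 21 |
| 21 | 140 | 20 |
| 28 | 133 | 19 |

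At L = 28 the cut-off is 168 − 133 = 35 days short of 24 weeks: 7 from the tolerance and 28 from the lead.

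**5. Which scans fall on days 133 to 160.**
- 12-weekly within ±7 days: none. The latest first scan is day 84 + 7 = 91, and the earliest second scan is day 168 − 7 = 161.
- 8-weekly within ±7 days: none (112 + 7 = 119; 168 − 7 = 161).
- 6- and 9-weekly: none on time. Each has a scan due on day 126, which reaches day 133 if 7 days late and then needs L = 28.
- On-time 4-, 5- and 10-weekly: day 140. On-time 7-weekly: day 147. On-time 11-weekly: day 154.
- A second 12-weekly scan done 8 to 35 days early: day 160 to 133.
- End-of-treatment (EOT) and unscheduled scans: possible on any of these days.

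**6. The further condition.** A scan in the gap changes nothing by itself. The patient must also have no SD or Non-CR/Non-PD scan on or after day 161, and no CR or PR that already counts. A 4-weekly patient with SD on days 140 and 168 qualifies under either origin.

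**7. A patient who does change.** SD on day 84, treatment stopped, SD at the EOT scan on day 140, no later scan, never CR or PR. The footnote to protocol Table 7-3 requires that EOT scan, since 140 − 84 = 56 days exceeds 28. Counted from first dose, 140 < 161 and the patient is not in CBR. Counted from consent, the patient is in CBR if L ≥ 161 − 140 = 21 days.

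**8. Confirmation.** Take a single PR at week 12 and progression at week 24. ORR states no confirmation, so on its face the patient counts. In CBR the patient fails if the word confirmed covers PR, and counts if it covers CR only. The SAP wording allows both readings.

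**The case against.** The strongest reply is that the consent reading is not established. Section 7.1.2.2 and SAP 2.1.1 point to patients past screening. The amendment rationales, taken only as evidence of usage, report 3,255 enrolled and 3,246 treated; a difference of 9 is hard to square with counting every signed consent. If enrollment means treatment assignment through the IRT shortly before dosing, the lead could be much shorter. This stands. A reader might infer that the SAP times SD from consent; the documents support only that it uses an undefined term that differs from treatment start.

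Two other stronger readings also fail. One is that the protocol requires unconfirmed response. Protocol 10.5.1 is silent, and Appendix 14.3.17 says that best response in general depends on confirmation criteria while making confirmation optional for a trial of this kind. The other is that SAP Section 4 is wrong because it omits the confirmation rule. Appendix 14.3.30 allows study-specific choices to be made in the analysis plan, so choosing an optional rule there is not clearly a change from the protocol.

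Nor is 28 days a firm cap: protocol 7.1.2 limits when screening assessments are done, sets no explicit maximum from consent to dose, and allows one re-screening.

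None of this supplies a defined origin for SD, or explains why CBR and ORR differ on confirmation.

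**Conclusion.** The point holds as an undefined and inconsistent rule. Followed as written and read as consent, it could credit as little as 19 weeks on treatment as 24 weeks of SD, given an assumed lead of 28 days. Only patients who meet the condition in step 6 are affected, and patients scanned 12-weekly within 7 days of schedule are not. The confirmation mismatch stands whether the word covers CR only or both CR and PR.

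If enrollment precedes first dose, moving to treatment start can only remove SD or Non-CR/Non-PD cases from CBR, while dropping confirmation can only add CR or PR cases. The documents give neither the consent-to-dose interval nor the rate of unconfirmed response, so the net effect cannot be computed. CBR is descriptive: no hypothesis test, sample size or safety result is affected.

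**What to change.** - In both sentences of the CBR paragraph in SAP 2.7.1, replace enrollment with the date of first study treatment, which SAP 2.1.3 already defines.
- State one confirmation rule for ORR and CBR, and say whether it covers CR, PR or both. Either choice is acceptable if it is the same for both.
- Describe the one-week tolerance as a SAP allowance. Protocol 7.1 gives a general window of ±3 days, and ±7 days appears only as an example in Appendix 14.3.17.
- If a time origin other than treatment start is kept, list it in SAP Section 4.

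The cost is a few wording edits and one start-date variable in the CBR derivation. Every patient in the Full Analysis Set has been dosed, so no new data are needed, and sample size and timelines do not change.
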